# 6.6.2 Safety Labs

Summaries and analyses of clinical safety labs are the same as specified in the M-SAP with the revision that lab results collected more than 28 days after last dose of study drug will not be tabulated, that abnormal levels will be classified to a toxicity grade based on quantitative grading using National Cancer Institute (NCI) Common Terminology Criteria for Adverse Events (CTCAE) version 5.0, and with the addition that maximum toxicity over all post-baseline visits that occur within 28 days or fewer after last dose of study drug will be included in shift tables along with visit-specific shifts.

The proportion of participants with TSH ≥10 mIU/L and the proportion with signs or symptoms of hypothyroidism will be presented as shift tables vs. the status of each participant at baseline for each visit and over all post-baseline visits that occur within 28 days or fewer after last dose of study drug by treatment group in all safety samples. The absolute level and the absolute change from baseline for free T3, free T4, and TSH will be summarized as means, standard deviations, medians, and ranges at each visit by treatment group in all safety samples.

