9 SAFETY AND ADVERSE EVENTS

9.1 Adverse Events of Special Interest – Thyroid Function

Reversible changes in thyroid function tests were observed during the preclinical studies and clinical studies with verdiperstat. Based on prior trials, a small percentage of participants may be expected to develop mild (subclinical) hypothyroidism generally with serum TSH < 10 mIU/L. Laboratory monitoring of thyroid function will be performed and documented throughout this study. Site Investigators should review TSH levels and note the trend over time. The Central Laboratory will flag any TSH \geq ULN, and T3 and free T4 analysis should be performed.

Any significant abnormal findings should be discussed with the study Medical Monitor and may be followed up as per local practice (e.g., investigations and consultation with endocrinologist). In cases of suspected hypothyroidism, repeat thyroid function tests should be measured and levothyroxine replacement therapy should be considered. Initiation of treatment is at the discretion of the SI.

Potential initiation of levothyroxine (T4) replacement therapy may be considered according to the following guidelines:

- For a serum TSH between 5 and 10, levothyroxine 0.05 mg daily (50 mcg) is a reasonable dose to prescribe.
- For a serum TSH between 10 and 20, levothyroxine 0.075 mg daily (75 mcg) is a reasonable dose to prescribe.
- For a serum TSH greater than 20, many physicians would feel more comfortable having an endocrinologist treat such participants.

If signs/symptoms of hypothyroidism (i.e. adverse event, initiation of levothyroxine) and/or significant changes in thyroid function develop, collection of follow up clinical chemistry samples and/or unscheduled study visits may be warranted. It is recommended to wait for 5 or 6 half-lives (5 – 6 weeks) to retest thyroid function. Serum T3, free T4 and TSH should be monitored in such participants, and the serum TSH assesses whether therapy is adequate.

If there are clinically significant issues with tolerability that are not able to be treated adequately with levothyroxine replacement therapy, the SI may consider modifications to the dosage regimen. Consultation with the Medical Monitor is required. Modifications may include reducing the dose of verdiperstat /matching placebo to 300 mg BID or taking a dose holiday. Any such modifications to the dosage regimen should be noted in the CRF.

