# 4.3 Safety Endpoints

In addition to the safety endpoints described in the M-SAP, the following RGB regimen-specific safety endpoint will be evaluated:

• Thyroid function: Proportion of participants with TSH ≥10 mIU/L, proportion of participants with signs or symptoms of hypothyroidism, and levels of free T3, free T4, and TSH.

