### **5.13 Clinical Safety Laboratory Tests**

Clinical safety labs include hematology, blood chemistry panel, liver function tests, thyroid function, urinalysis, and pregnancy testing in women of childbearing potential as specified in Section 9.1.2 Clinical Safety Laboratory Tests of the Master Protocol:

- Hematology: hematocrit, hemoglobin, platelet count, red blood cell (RBC) count, mean
  corpuscular volume, mean corpuscular hemoglobin, mean corpuscular hemoglobin
  concentration, RBC distribution width (RDW), RBC morphology, white blood cell (WBC)
  count, and counts and percentages of basophils, eosinophils, lymphocytes, monocytes, and
  neutrophils;
- Blood chemistry panel: bicarbonate, chloride, potassium, sodium, calcium, magnesium, phosphate, blood urea nitrogen, creatinine, estimated glomerular filtration rate (eGFR) calculated using the Modification of Diet in Renal Disease (MDRD) four-variable equation, creatinine clearance calculated using the Cockcroft-Gault equation, and glucose;
- Liver function tests: alanine aminotransferase (ALT [SGPT]), aspartate aminotransferase (AST [SGOT]), alkaline phosphatase (ALP), albumin, total protein, total bilirubin (TBL);
- Thyroid function tests: thyroid-stimulating hormone (TSH), reflex T3 and T4 when TSH levels are abnormal;
- Urinalysis: clarity, color, specific gravity, pH, microalbumin, protein, glucose, ketones, bilirubin, urobilinogen, nitrite, leukocyte esterase, and blood; and
- Pregnancy: qualitative and quantitative serum human chorionic gonadotropin (hCG).

Clinical safety labs will also include derived measures of potential drug-induced liver injury (DILI), including those that potentially meet the Hy's law criteria, as distinct safety lab outcomes.

Three potential DILI criteria will be defined:

- ALT or AST >3x ULN with TBL >1.5x ULN
- AST or ALT >3x ULN with TBL >2x ULN
- AST or ALT >3x ULN with TBL >2x ULN and ALP <2x ULN (potential Hy's Law cases) where ULN is upper level of normal and all levels are measured on the same day.

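### The planned by-arm means and changes from baseline for free T3 and free T4 compare only participants selected by an abnormal TSH, which the drug itself can raise, so the difference between arms does not show the drug's effect on these hormones

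*SAP*

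**What the plan says.** SAP 4.3 adds thyroid function as a regimen-specific safety endpoint. Besides TSH of 10 mIU/L or more and signs or symptoms of hypothyroidism, it includes "levels of free T3, free T4, and TSH". SAP 6.6.2 sets out the summary: "The absolute level and the absolute change from baseline for free T3, free T4, and TSH will be summarized as means", followed by "standard deviations, medians, and ranges at each visit by treatment group in all safety samples". The three analytes are treated alike.

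The testing rules do not treat them alike. Footnote 8 of the placebo-controlled Schedule of Activities, in both the protocol and SAP 2.9, lists thyroid function as TSH only. SAP 5.13 describes "reflex T3 and T4 when TSH levels are abnormal" and attributes the panel to "Section 9.1.2 Clinical Safety Laboratory Tests of the Master Protocol". Protocol 9.1 has the central laboratory flag a TSH at or above ULN, "and T3 and free T4 analysis should be performed". It also calls for T3 and free T4 when suspected or treated hypothyroidism is followed up. Neither document schedules T3 or T4 for everyone at baseline or at any later visit.

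**The concern.** Whether a participant has a T3/T4 value at a visit is decided after randomisation, mainly by TSH. Protocol 5.9.1.1 reports that in earlier studies verdiperstat was associated with rising mean TSH and some falls in mean free T4 and free T3, relative to placebo. The drug can therefore change who enters the free T3 and free T4 rows, and the tested active and tested placebo participants are not comparable groups.

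Change from baseline adds a second filter, because it also needs a T3/T4 result at baseline. A participant with normal TSH at baseline who becomes abnormal on treatment is the case of most interest, and would ordinarily have no baseline value.

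Thyroid function is this regimen's adverse event of special interest. Readers will look at these rows to see whether the earlier fall in free T4 and free T3 recurs, and the difference between arms in these rows does not answer that.

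**Working it through.** The plan gives no figure for these rows, so there is nothing to reproduce. The finding rests on the text; the arithmetic shows how much could be at stake.

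**1. Testing rule against summary**

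| | TSH | Free T3, free T4 |
|---|---|---|
| Scheduled for everyone | Yes (footnote 8, both schedules) | No |
| When measured | Each safety-lab visit | After abnormal TSH, or in hypothyroidism follow-up (SAP 5.13; protocol 9.1) |
| Planned summary | Level and change, by arm and visit, all safety sets | The same |

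**2. Inputs.** From the documents: 120 active and 40 placebo. Assumed: median TSH 1.8, log-SD 0.5, ULN 4.5, free T4 SD 0.15, correlation ρ of log TSH with free T4 from −0.2 to −0.6, and visit-to-visit TSH correlation r from 0.5 to 0.85. Testing is modelled only as TSH at or above ULN at that visit.

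**3. Who is tested.** If treatment multiplies TSH by m, the share tested is 1 − Φ(z), with z = [ln 4.5 − ln(1.8m)]/0.5.
- Placebo, m = 1: z = 1.833, 3.3%, or 1.3 of 40.
- Active, m = 1.4: 12.3%, or 15 of 120. With m = 1.6: 18.6%, or 22 of 120.
- 30% responders with m = 2: 0.7 × 0.0334 + 0.3 × 0.3277 = 12.2%, or 15 of 120; 81% of those tested are responders.
- 50% responders with m = 2: 18.1%, or 22 of 120.

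**4. Direction of bias.** Among those tested, mean free T4 is its arm mean plus ρ × 0.15 × λ(z), where λ(z) = φ(z)/[1 − Φ(z)]. Observed active-minus-placebo differences in level:

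| Assumed effect | True difference | ρ = −0.2 | ρ = −0.4 | ρ = −0.6 |
|---|---|---|---|---|
| Uniform, TSH +40% | −0.05 | −0.033 | −0.016 | +0.001 |
| Uniform, TSH +60% | −0.05 | −0.026 | −0.003 | +0.021 |
| Uniform, TSH +40% | −0.10 | −0.083 | −0.066 | −0.049 |
| Uniform, TSH +60% | −0.10 | −0.076 | −0.053 | −0.029 |
| 30% responders, TSH doubled, free T4 −0.20 | −0.060 | −0.134 | −0.107 | −0.080 |
| 50% responders, TSH doubled, free T4 −0.15 | −0.075 | −0.106 | −0.075 | −0.044 |

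A uniform effect is diluted or even reversed. An effect concentrated in responders can be overstated. The documents do not say which applies.

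**5. Sparsity, regimen-only set (40 placebo).** With share p at or above ULN, P(fewer than two values) = (1 − p)^40 + 40p(1 − p)^39. This is 81% at p = 2%, 61% at 3.3% and 30% at 6%.

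For change from baseline, let q be the probability that both baseline and visit TSH reach ULN (bivariate normal, correlation r). The placebo row is empty with probability (1 − q)^40:

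| p | q, r = 0.5 | Empty | q, r = 0.85 | Empty |
|---|---|---|---|---|
| 2% | 0.0034 | 87% | 0.0099 | 67% |
| 3.3% | 0.0069 | 76% | 0.0177 | 49% |
| 6% | 0.0157 | 53% | 0.0345 | 25% |

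In the active arm, with baseline share 3.3% and the effects in step 3, 1.5 to 3.8 of 120 have both values. Of the active participants tested at that visit, 76% to 91% have no baseline value.

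**6. Sparsity with shared placebo.** The full safety set (STF) adds placebo from regimens A and C. If each contributes about 40 (assumed), placebo n is about 120. At p = 3.3%, P(fewer than two values) falls to about 9%, and an empty change row to 12%–43%. The formulas in steps 3 and 4 do not contain n, so the selection is unchanged.

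**The case against.** The strongest reply is that SAP 6.6.2 plans only description. It sets no contrast, interval or test for these rows, and no decision rule uses them. The thyroid signal is covered elsewhere: TSH level and change, shift tables for TSH of 10 mIU/L or more and for signs or symptoms, graded laboratory shifts, and adverse events of special interest with rate differences and confidence intervals. That stands, and it limits the weight of the point.

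Reflex values are also useful in themselves. Among participants with raised TSH they show whether free T4 is low. A reader might infer that the rows are worthless; they are not. What they cannot support is a comparison between arms.

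Every numerical input except the 120:40 split is assumed. The modelled 12% to 19% of active participants tested at one visit sits awkwardly with protocol 9.1, where "a small percentage of participants may be expected to develop mild (subclinical) hypothyroidism". The model also omits follow-up testing and any reflex after a low TSH. The counts are therefore illustrations. A reader might infer that the placebo rows will be empty, but the high probabilities apply to the 40-placebo set and fall once placebo is shared. A reader might also infer that the rows must hide a fall in free T4. That holds for the uniform effects modelled but not for all the responder cases.

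The Master SAP and the Master Protocol are not available, and the Master SAP's tables may print the number tested. That would reveal sparse cells but would not remove selection on TSH. SAP 5.13 presents its reflex rule as the Master Protocol's, so nothing available suggests universal T3/T4 testing.

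**Conclusion.** The point holds as a defect in a named, descriptive safety endpoint, and should be corrected. Following the current text yields by-arm free T3 and free T4 means and changes in subsets selected after randomisation on a variable the drug was reported to raise. Their difference does not show the drug's effect on T3 or T4, and the documents do not fix the sign of the bias.

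That conclusion needs only the testing rules and protocol 5.9.1.1. The size does rest on assumptions. In the regimen-only set, with 2% to 6% of placebo at or above ULN, fewer than two placebo values at a visit has probability 30% to 81%, and an empty placebo change row 25% to 87%. With about 120 placebo participants and a 3.3% share, these are about 9% and 12% to 43%.

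A reader might infer that the thyroid safety assessment as a whole, or the trial's main result, is compromised. The documents do not support that. The primary analysis, the TSH rows, the two shift tables and the adverse events of special interest do not depend on who had T3 or T4 measured.

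**What to change.** In SAP 4.3 and 6.6.2:
- Keep means and changes from baseline for TSH only.
- For T3/T4, report by arm and visit, over all treated participants: the number with TSH at or above ULN, the number reflex-tested, and the number with low free T4 among those tested. Do not count untested participants as normal.
- Present reflex values as a listing, or as a summary showing number tested out of number at risk. Label them as conditional on abnormal TSH and not for comparison between arms.
- Before including shared placebo participants, confirm that the reflex trigger in Master Protocol 9.1.2 also applied to them.

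An optional clean-up is to reconcile the wording. The analytes are free T3 and free T4 in SAP 4.3 and 6.6.2, T3 and T4 in SAP 5.13, and T3 and free T4 in protocol 9.1. The trigger is an abnormal TSH in SAP 5.13 and a TSH at or above ULN in protocol 9.1.

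The cost is text edits and one document check, with no new samples. The downside is that T3/T4 appear as counts and labelled values rather than by-arm means.

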#### 6.6.3 ECG Results

Summaries of ECG parameters and findings are the same as specified in the M-SAP with the revision that ECG parameters and findings collected more than 28 days after last dose of study drug will not be tabulated.

### 6.6.4 Vital Signs and Weight

Summaries and analyses of vital signs and weight are the same as specified in the M-SAP with the revision that vital signs and weight collected more than 28 days after last dose of study drug will not be tabulated.

#### 6.6.5 Suicidality

Summaries of suicidality are the same as specified in the M-SAP with the revision that suicidality noted more than 28 days after last dose of study drug will not be tabulated.

# 6.7 Other Analyses

# 6.7.1 Participant Disposition

All participants consented to the Master Protocol between the time of the first and last consent of a participant assigned to a regimen included in the FAS analysis set will be summarized as a single set for the following events: consented to the Master Protocol, failed screening for the Master Protocol, other reasons not assigned to a regimen (including timing out of the screening window, death, withdrawal of consent, early termination, and administrative termination), and assigned to a regimen. Reasons for Master Protocol screen failure will be summarized.

All participants in the above sample assigned to a regimen will be summarized as two sets (final screening for RGB vs. final screening for a non-RGB regimen) for the following events: consented to a regimen, failed screening for a regimen, other reasons not randomized within a regimen (including timing out of the screening window, death, withdrawal of consent, early termination, and administrative termination), and randomized within a regimen. If a given individual is screened multiple times prior to randomization within a regimen, then the final screening experience of that individual will be summarized. Reasons for RGB screen failure will be summarized separately for all participants screened for RGB whether that was their final screening experience or not.

All participants in the FAS analysis set will be summarized as two sets (randomization to active study drug vs. randomization to placebo) for the following events: initiated regimen-specific study drug, prematurely terminated study participation due to death, withdrawal of consent, early termination, loss to follow-up, or administrative termination, completed 24-week follow up, and completed a safety follow-up visit vs. continued into the OLE. Reasons for withdrawal of consent or early termination after randomization will be summarized.

Any randomized participants excluded from the FAS and EPP analysis sets or included in the FAS analysis set but not contributing to the primary analysis will be identified in a listing together with the reason for their exclusion.

### 6.7.2 Study Drug Compliance and Tolerance

Summaries of study drug compliance and tolerance are the same as specified in the M-SAP with the clarification that summaries will be reported for the ERO and SRO analysis sets and that date of permanent discontinuation of study drug is the date of last use of double-blind study drug among all participants in a given analysis set.

The number of days of exposure to study drug will be calculated in three ways:

- as the number of days from dose initiation to the final safety assessment during the placebocontrolled period, inclusive,
- as the number of days from dose initiation to drug withdrawal, inclusive, less any interval during which use of study drug was interrupted (individual missed doses will not be subtracted unless noted in the dosage management log), and
- as the number of days from dose initiation to the earlier of final contact during the placebocontrolled period or 28 days after last dose of study drug, inclusive.

Page 32 of 33

The proportion of participants who interrupted study drug or reduced study drug dosage and the time to first study drug interruption or dosage reduction will be summarized. The number of days of exposure to a reduced dosage of study drug will be summarized.

#### **6.7.3** Concomitant Medication Use

Summaries of concomitant medication use are the same as specified in the M-SAP with the clarification that medications taken at baseline and those initiated after first dose of study drug will be separately summarized and will be classified by ATC Therapeutic class and WHODrug Preferred base name.

# **6.7.4** Medical History

Medical histories will be summarized by MedDRA system organ class, high level term, and preferred term in the STF and SRO analysis sets.

#### 6.7.5 Blindedness

The proportions of participants and site investigators who report on the Exit Questionnaire a guess of active vs. placebo treatment assignment, each level of surety of that guess, and each of five pre-specified reasons for making a treatment assignment will be summarized by treatment group in the FAS and ERO analysis sets. Treatment-dependent differences in the proportion guessing active treatment assignment will be tested among all respondents and among those stating they are at least somewhat sure of their guess by Fisher's exact test and the difference in proportion guessing active treatment assignment will be estimated with confidence bounds.

#### 6.7.6 Protocol Deviations

The number of major and minor protocol deviations will be summarized by type of deviation and treatment group in all analysis sets. Listings of all protocol deviations will be produced.

### 6.7.7 Impact of COVID-19 Pandemic

The proportions of planned assessments missed due to COVID-19 restrictions or disruptions will be summarized by treatment group, visit, and type of assessment in the FAS and ERO analysis sets. Protocol deviations that resulted from COVID-19 restrictions or disruptions will be summarized by treatment group and type of deviation in the FAS and ERO analysis sets.

A listing will document participants with assessments missed due to COVID-19 restrictions or disruptions and those experiencing protocol deviations that resulted from COVID-19 restrictions or disruptions and will describe the manner affected by COVID-19.

### 7. Validation

#### 7.1 Primary Efficacy Analysis

Validation of the primary efficacy analysis is the same as specified in the M-SAP.

# 7.2 Secondary, Exploratory, and Safety Analyses

Validation of secondary, exploratory, and safety analyses are the same as specified in the M-SAP.

